**Important note (5):**

Below are the AEs specific to each drug, warnings/precautions and guidance for dose modifications/interruption of drugs.

**Palbociclib (IBRANCE):** (*reference USPI- IBRANCE*)

1. Capsules should be taken with food. Patients should be encouraged to take their dose of palbociclib at approximately the same time each day.
2. If the patient vomits or misses a dose, an additional dose should not be taken. The next prescribed dose should be taken at the usual time. Palbociclib capsules should be swallowed whole (do not chew, crush or open them prior to swallowing). Capsules should not be ingested if they are broken, cracked, or otherwise not intact.
3. It is known there is a potential for palbociclib to increase the exposure of axitinib through a time-dependent CYP3A4 mediated drug-drug interaction. As a weak time-dependent CYP3A4 inhibitor, palbociclib may reduce the clearance of axitinib, which may increase its exposure-related toxicities. Therefore, it is advised to: Exclude patients currently taking strong CYP3A4 inducers and inhibitors if an alternative concomitant medication cannot be used because they will increase the variability in PK for both axitinib and palbociclib, See [Appendix 9](#).
4. Exclude patients with moderate hepatic impairment from the dose escalation phase of the study or until the MTD for the combination regimen has been determined. The combined effect of CYP3A4 inhibition by palbociclib along with the reduced clearance observed in patients with moderate hepatic impairment on the PK of axitinib is unknown. See US package insert (PI) for axitinib for further details,
5. Exclude patients currently taking proton pump inhibitors from the study due to their impact on the disposition of palbociclib during the dose escalation phase. Patients taking H2-receptor blockers and local antacids can be included in the dose escalation portion of the study as these classes of agents do not alter the PK of palbociclib.
6. Grapefruit or grapefruit juice intake during the whole duration of the treatment should be avoided as it may increase concentration of the drug in blood.

### Toxicity management

The most common ( $\geq 2\%$ ) Grade  $\geq 3$  adverse reactions of palbociclib were neutropenia, leukopenia, anaemia, fatigue, and infections

1. Monitor complete blood counts prior to starting palbociclib therapy and at the beginning of each cycle, as well as on Day 14 of the first 2 cycles, and as clinically indicated
2. Dose interruption, dose reduction or delay in starting treatment cycles is recommended for patients who develop Grade 3 or 4 neutropenia
3. Special warning is febrile neutropenia has been reported in about 1% of patients exposed to palbociclib.
4. Guidelines for dose adjustments for hematologic toxicities attributable to palbociclib
  - Grade 3: No dose adjustment is required. Consider repeating complete blood count monitoring one week later. Withhold initiation of next cycle until recovery to Grade  $\leq 2$ .
  - Grade 3 ANC ( $<1000$  to  $500 \text{ mm}^3$ ) + Fever  $\geq 38.5^\circ\text{C}$  and/or infection: Withhold palbociclib and initiation of next cycle until recovery to Grade  $\leq 2$  ( $\geq 1000/\text{mm}^3$ ). Resume at next lower dose.
  - Grade 4: Withhold palbociclib and initiation of next cycle until recovery to Grade  $\leq 2$ . Resume at next lower dose

### **Axitinib (INLYTA) (reference USPI-INLYTA)**

1. Administer axitinib doses approximately 12 hours apart with or without food. Axitinib should be swallowed whole with a glass of water.
2. If the patient vomits or misses a dose, an additional dose should not be taken. The next prescribed dose should be taken at the usual time.
3. It is known there is a potential for palbociclib to increase the exposure of axitinib through a time-dependent CYP3A4 mediated drug-drug interaction. As a weak time-dependent CYP3A4 inhibitor, palbociclib may reduce the clearance of axitinib, which may increase its exposure-related toxicities. Therefore, it is advised to: Exclude patients currently taking strong CYP3A4 inducers and inhibitors if an alternative concomitant medication cannot be used because they will increase the variability in PK for both axitinib and palbociclib, [see Appendix 9](#).
4. Exclude patients with moderate hepatic impairment from the dose escalation phase of the study or until the MTD for the combination regimen has been determined. The combined effect of CYP3A4 inhibition by palbociclib along with the reduced clearance observed in patients with moderate hepatic impairment on the PK of axitinib is unknown
5. Grapefruit or grapefruit juice intake during the whole duration of the treatment should be avoided as it may increase concentration of the drug in blood.

### Toxicity management

The most common ( $\geq 20\%$ ) adverse reactions are diarrhea, hypertension, fatigue, decreased appetite, nausea, dysphonia, palmar-plantar erythrodysesthesia (hand-foot) syndrome, weight decreased, vomiting, asthenia, and constipation.

1. Blood pressure should be well-controlled prior to initiating axitinib. Patients should be monitored for hypertension and treated as needed with standard anti-hypertensive therapy. The median onset time for hypertension (systolic blood pressure  $>150 \text{ mmHg}$  or diastolic blood pressure  $>100$

mmHg) was within the first month of the start of axitinib treatment and blood pressure increases have been observed as early as 4 days after starting. In the case of persistent hypertension despite use of anti-hypertensive medications, reduce the axitinib dose. Discontinue axitinib if hypertension is severe and persistent despite anti-hypertensive therapy and dose reduction of axitinib, and discontinuation should be considered if there is evidence of hypertensive crisis. If axitinib is interrupted, patients receiving antihypertensive medications should be monitored for hypotension

2. Use axitinib with caution in patients who are at risk for, or who have a history of, arterial thromboembolic events (including transient ischemic attack, cerebrovascular accident, myocardial infarction, and retinal artery occlusion). Axitinib has not been studied in patients who had an arterial thromboembolic event within the previous 12 months.
3. Use axitinib with caution in patients who are at risk for, or who have a history of venous thromboembolic events. Axitinib has not been studied in patients who had a venous thromboembolic event within the previous 6 months.
4. Axitinib should not be used in patients with recent active gastrointestinal bleeding. If any bleeding requires medical intervention, temporarily interrupt the axitinib dose.
5. Monitor for symptoms of gastrointestinal perforation or fistula periodically throughout treatment with axitinib.
6. Monitor thyroid function before initiation of, and periodically throughout, treatment with axitinib. Treat hypothyroidism and hyperthyroidism according to standard medical practice to maintain euthyroid state.
7. Discontinue axitinib in patients developing Reversible Posterior Leukoencephalopathy Syndrome (RPLS). RPLS is a neurological disorder which can present with headache, seizure, lethargy, confusion, blindness and other visual and neurologic disturbances. Mild to severe hypertension may be present. Magnetic resonance imaging is necessary to confirm the diagnosis of RPLS. The safety of reinitiating axitinib therapy in patients previously experiencing RPLS is not known.
8. Monitoring for proteinuria before initiation of, and periodically throughout, treatment with axitinib is recommended. For patients who develop moderate to severe proteinuria, reduce the dose or temporarily interrupt axitinib treatment.
9. Monitor ALT, aspartate aminotransferase (AST) and bilirubin before initiation of and periodically throughout treatment with axitinib.
10. Monitor for cavitation apparition throughout the treatment with axitinib.

## Avelumab (BAVENCIO)

**Premedication:** Premedication for the first four doses of avelumab is mandatory. An antihistamine and paracetamol (acetaminophen) 30 to 60 minutes prior to the first 4 doses of avelumab is preferred (for example, 25-50 mg diphenhydramine and 500-650 mg paracetamol IV or oral). Equivalents of these drugs can be used in case of allergy or other contraindication. Premedication should be administered for subsequent avelumab doses based upon clinical judgment and presence/severity of prior infusion reactions.

Premedication may be modified based on local treatment standards and guidelines, as appropriate. Examples of premedication options include but are not limited to nonsteroidal anti-inflammatory drugs as well as non-sedating anti-histamines like Zyrtec (cetirizine hydrochloride).

**Setting:** Avelumab should be administered in a setting that allows for immediate access to an intensive care unit or equivalent environment and administration of therapy for anaphylaxis, such as the ability to

implement immediate resuscitation measures. Steroids (dexamethasone 10 mg), epinephrine (1:1,000 dilution), allergy medications (IV antihistamines), bronchodilators, or equivalents, and oxygen should be available for immediate access.

**Instructions for Storage:** Avelumab drug product must be stored at 2 °C to 8 °C until use and protected from light. Avelumab stored at higher temperatures for extended periods of time might be subject to degradation. Avelumab drug product must not be frozen. Rough shaking of the solution must be avoided.

**Instruction for Preparation:** Avelumab drug product must be diluted with 0.9% saline solution (sodium chloride injection) supplied in an infusion bag; alternatively a 0.45% saline solution can be used if needed. The diluted solution is stable 8h at room temperature and up to 24h at 2–8 °C.

Prior to the preparation of the dilution for final infusion, allow each vial to equilibrate to room temperature. Use a disposable syringe equipped with a needle of suitable size to remove a volume of sodium chloride solution to be replaced by avelumab from the infusion bag and discard the removed solution. Use a new disposable syringe equipped with a needle of suitable size to inject a volume of avelumab drug product identical to the discarded volume of sodium chloride solution into the infusion bag. Gently invert the mixture 10 times. Infusion bags must not be shaken, in order to avoid foaming or excessive shearing of the protein solution. The preparation must be carefully inspected as it should result in a homogeneous looking clear solution, free of visible particles.

Avelumab should be administered as an approximately 90 to 120 minutes infusion for the first administration to avoid infusion-related reactions. For subsequent doses, it can be administered as a 60 min or longer infusion.

#### **Toxicity Management (see Table 2, Table 3 and Table 4, in appendix 6):**

Adverse Drug Reactions requiring avelumab discontinuation or modification ([Table 2](#))

Treatment Modification for Symptoms of Infusion-Related Reactions ([Table 3](#))

Management of immune-mediated adverse reactions ([Table 4](#))

Understanding contribution of each of the three drugs in observed toxicities, and manage dose reductions.

**Observation period:** Following avelumab infusions, patients must be observed for 30 minutes post-infusion for potential infusion-related reactions.

### **ADVERSE DRUG REACTIONS REQUIRING AVELUMAB DISCONTINUATION OR MODIFICATION**

Dose escalation or reduction is not recommended. Dosing delay or discontinuation may be required based on individual safety and tolerability ([refer to Appendix 6](#)). Resume avelumab in patients whose adverse reactions recover to Grade 1 or resolved.

**Any Grade 4 ADRs require permanent treatment discontinuation with avelumab** except for single laboratory values out of normal range that are unlikely related to study treatment as assessed by the Investigator, do not have any clinical correlate, and resolve within 7 days with adequate medical management and endocrinopathies controlled with hormone replacement.

**Recurrent Grade 3 ADRs and Grade 3 infusion-related reaction require permanent discontinuation.**

**Any Grade 2 ADR should be managed as follows:**

- If a Grade 2 ADR resolves to Grade  $\leq$  1 by the last day of the current cycle, treatment may continue.
- If a Grade 2 ADR does not resolve to Grade  $\leq$  1 by the last day of the current cycle, infusions should not be given on the following cycle. If at the end of the following cycle the event has not resolved to Grade 1, it should be treated as a Grade 3 or 4 (except for hormone insufficiencies, that can be managed by replacement therapy; for these hormone insufficiencies, up to 2 subsequent doses may be omitted).
- Upon the second occurrence of the same Grade 2 ADR (except for hormone insufficiencies that can be managed by replacement therapy) in the same subject, treatment with avelumab has to be permanently discontinued.

Important note (6):	Specific protocol dose modification for toxicity management related to palbociclib: 

- In case of recurrent grade 3 hematologic toxicities, palbociclib may be reduced to 75 mg po daily one week off and one week on.

- In case of other severe (<math>\geq</math> grade 3) toxicity related to palbociclib, consider holding palbociclib until toxicity is grade 1 or less, then resume at the alternate schedule of 2 weeks OFF / 2 weeks ON.

----------------------------	---

- **DLT will be defined as:**

Any of the following events that are considered to be clinically significant and meaningful as per evaluation of the attending physicians and confirmed by CMC and at least possibly related to drug. DLTs for the purposes of dose-escalation will be evaluated during the 28-day period following the first dose of study treatment. Each treatment cycle is four weeks. Toxicities will be graded and documented according the NCI CTCAE (v4.03).

- **Non-hematological dose-limiting toxicity is defined as:**

- Persistent Grade 3 or 4 hypertension despite treatment with anti-hypertensive drugs.
- Grade 3 or 4 Gastrointestinal bleeding.
- Grade 3 or 4 Gastrointestinal perforation or fistula.
- Development of Reversible Posterior Leukoencephalopathy Syndrome.
- Persistent Grade 3 or 4 proteinuria.
- Grade 3 or 4 arterial or venous thromboembolic events.
- Any other Grade 3 or Grade 4 non-hematological toxicity that are considered at least possibly related to a study drug and clinically significant after discussion at CMC with exceptions listed below:  
grade 3 nausea, vomiting, diarrhea, that responds to maximal supportive treatment(s) within 3 days, grade 3 liver enzyme elevation, including ALT/AST/GGT that returns to Grade  $\leq 1$  or baseline prior to the time for the next treatment cycle.
- Allergic reactions that necessitate discontinuation of the study drug responsible for the reaction.
- Any Grade  $\geq 2$  pneumonitis of any duration.

- **Hematological dose-limiting toxicity is defined as:**

- Grade 4 neutropenia (absolute neutrophil count, ANC) for  $> 7$  days
- Platelet count  $< 10,000/\text{mm}^3$  one time or bleeding requiring transfusion
- Toxicity that causes a delay of  $> 14$  days between treatment cycles
- Febrile neutropenia despite G-CSF secondary prophylaxis
- Either isolated or recurrent (i.e., cardiac, renal, neurologic) toxicity that is judged by the Investigator to be a DLT.

- **Further evaluation of the combination's toxicity at a dose level:**

Up to 3 additional patients could be added at a dose level to explore the toxicity on an occasional basis after discussion with the CMC. All additional patients will be included in the study's assessment.

- **To decide for dose-escalation cohort at a higher dose level,** the CMC that includes the study investigators and the sponsor clinical study team, will review available data (e.g. safety profile). Subsequent safety reviews by the CMC will be conducted prior to enrollment of patients in a new cohort and to establish the RP2D.

- **Intra-patient dose escalation:**

Patients will be permitted to have a dose escalation to the highest dose shown to be safe at the time of escalation, provided they have no clinically relevant drug-related toxicity  $>$  Grade 1 at the dose

level they are on and that both they and their physician deem a dose escalation to be in their interest. For a dose level to be considered proven safe, there must be at least three patients treated at that dose level for at least four weeks, and the clinical monitoring committee must have deemed that dose level to be at or below the MTD.

- **Dose reduction**

Patients who have a dose limiting toxicity and it is unclear as to which drug may have caused the toxicity, may restart drugs at the next lower dose level once toxicity returns to  $\leq$  Grade I. If the investigator deems the toxicity to be due to one of the drugs in the regimen, only that drug may need to be reduced to the next lower dose level. A second dose reduction of this type may occur if toxicity recurs. For a patient who is responding (PR or CR) the investigator may continue to reduce the dose to the lowest dose level tolerable; for these responding patients, if one drug is deemed responsible for recurring serious toxicity, it may be stopped and the other two drugs continued after review by the clinical monitoring committee.

### 3.3.2. The Phase 2

When the recommended Phase 2 dose is reached, there will be a first expansion of the study to explore efficacy of the tested triple combination. In the expansion, only patients with unresectable or metastatic NSCLC with no prior treatment line will be treated. Up to 100 patients will be treated with the combination (~120 patients enrolled\*) until progression. For ethical reasons, even patients who failed biopsy(ies) will be treated with the triple-therapy. Pending clinical activity, the study may be extended (with a study amendment) to an additional 100 patients treated in phase 2 in order to attain sufficient statistical power to support the validity of the approach.

Study participation will be offered to patients with locally advanced or metastatic disease. Patients with documented oncogenic aberrations (EGFR, ALK, ROS1 if available, MET exon 14 skipping if available) at enrollment will be excluded from the trial. In the case of patients already treated on SPRING protocol who are later determined to have EGFR mutation or ALK translocation or ROS1 or MET exon 14 skipping mutations after SIMS analyses, they will be asked to re-consent. Patients will be included in the study regardless of their PD1 or PD-L1 expression status. Main outcome variables will include response rate (RR), progression-free survival (PFS), and overall survival (OS).

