Important note (3)	
A key point will be to understand the contribution of each of the drugs in generating toxicities. To this purpose, the CMC will specifically investigate whether observed toxicities relate to overlapping effects (such as fatigue, nausea diarrhea) or specific toxicities (such as febrile neutropenia – palbociclib) or low platelets level (axitinib). Appendix 8 describes all observed toxicities and outlines common or specific toxicities. Main toxicities specific to each drug are summarized in Important note (5).
 
Rules in case of toxicity/dose modifications:
 
For any Grade 3 dose-limiting toxicity (see page 32 for dose-limiting toxicity definitions) that is deemed to be drug specific, that drug will be held until resolution to <Grade 1. The drug will then be restarted with the dose at the next lowest level. If Grade 3 or greater toxicity recurs, the drug will be permanently stopped. Exception is hematologic toxicity which may be handled as in Important note (5), palbociclib section or Important note (6).
 
If a toxicity has been deemed to be due to a single drug, but persists at <math>\geq</math> grade 3 level after stopping the drug, all drugs will be stopped.
 
If it is unclear as to the drug that is causing a toxicity, all three drugs will be held.

	
Toxicities that may be clearly attributable to avelumab include immune toxicities such as immune mediated pneumonitis, hepatitis, colitis and nephritis, and infusion related reactions.
 
Toxicities clearly attributable to axitinib include hypertension and proteinuria.
 
Toxicities clearly attributable to palbociclib include lowering of white blood cells (WBC) or platelet counts.
 
For Grade 4 dose limiting toxicities, the drug to which it is attributable will be permanently stopped. If it is not clear as to which drug is associated with the toxicity, all drugs will be permanently stopped.
 
A Clinical Monitoring Committee (that includes site PIs) may be convened to help decide to which drug the toxicity is attributable.

Important note (4)	For dose interruption and reduction events, accurate medical administration records will be maintained to capture changes in dosing regimens, including concomitant medications.

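### After a recurrent non-hematologic DLT of Grade 3 or greater, one dose rule requires a permanent stop while others allow re-dosing, and no text says which prevails

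*Combined protocol and SAP*

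**What the plan says.** All the rules are in section 3.3.1.

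- **Important note (3)**, on a drug-specific Grade 3 DLT: hold the drug, restart it one level lower, and then "If Grade 3 or greater toxicity recurs, the drug will be permanently stopped". The carve-out reads "Exception is hematologic toxicity which may be handled as in", pointing to notes (5) and (6).
- **Important note (3)**, on Grade 4: "For Grade 4 dose limiting toxicities, the drug to which it is attributable will be permanently stopped". For unclear cause: "If it is not clear as to which drug is associated with the toxicity, all drugs will be permanently stopped".
- **Important note (6)**, second bullet: for other palbociclib-related toxicity of Grade 3 or more, consider holding the drug until Grade 1 or less, "then resume at the alternate schedule of 2 weeks OFF / 2 weeks ON". It sets no upper grade and no limit on recurrence.
- **Dose reduction paragraph**, for a patient with a DLT of unclear cause: the patient "may restart drugs at the next lower dose level once toxicity returns to" Grade 1 or less. If one drug is held responsible, "only that drug may need to be reduced to the next lower dose level". Then: "A second dose reduction of this type may occur if toxicity recurs". None of these sentences gives a grade. For responders (PR or CR), reduction may continue to the lowest tolerable level. One drug responsible for recurring serious toxicity may be stopped and the other two continued after CMC review.

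**The concern.** The non-hematologic DLT definition includes Grade 3 and Grade 4 events, so these paragraphs cover the same patients. Note (3) is mandatory; the others are permissive. A site that re-doses after a recurrent Grade 3 event can point to written permission, and a site that stops can point to a written order.

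Patient safety and consistent handling across sites are at stake in a first dose-finding study of this triplet. Section 3.3.2 gives no separate modification rules for Phase 2, so the same text would presumably apply there too.

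**Working it through.** The plan states no figure to reproduce. The check compares the rules by type of event and then shows how far apart the resulting doses are.

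**Side by side, non-hematologic DLTs**

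| Event | Note (3) | Dose reduction paragraph | Note (6), palbociclib only |
|---|---|---|---|
| First Grade 3, one drug | Hold, restart lower | Reduce that drug | Hold, alternate schedule |
| Recurrence at Grade 3 or greater, one drug | Permanent stop | Second reduction allowed | Resumption not excluded |
| Grade 4, one drug | Permanent stop | Reduction, no grade limit | Resumption not excluded |
| Grade 4, cause unclear | Stop all drugs | Restart lower, no grade limit | Not applicable |

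The first row has no permanent-stop conflict. The second is a direct clash. The last two overlap on the literal text.

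The clash needs a recurrence of Grade 3 or greater attributed to one drug. The second-reduction sentence directly follows the single-drug sentence, so that is its natural subject. A recurrence below Grade 3 raises no conflict. For a recurrent Grade 3 event of unclear cause, note (3) orders a hold and states no recurrence rule.

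**Doses per 28 days.** Inputs are the dose-level table in the Treatment Plan: palbociclib 125, 100 or 75 mg for 21 days (levels 4, 3 and 2), and axitinib 5 mg twice daily at levels 2 to 4, 3 mg at level 1 and 2 mg at level -1. The alternate schedule has 14 dosing days. I assume the daily dose is unchanged on that schedule, and that for a single drug the next lower level means its next lower dose in the table.

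*Recurrence, palbociclib started at 125 mg (planned 125 × 21 = 2625 mg), already reduced to 100 mg:*
- Note (3): 0 mg.
- Dose reduction paragraph: 75 × 21 = 1575 mg (1575/2625 = 60% of planned).
- Note (6): 100 × 14 = 1400 mg (1400/2625 = 53%).

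*Recurrence, palbociclib started at 100 mg (planned 100 × 21 = 2100 mg), already reduced to 75 mg:*
- Note (3): 0 mg.
- Dose reduction paragraph: no lower palbociclib dose exists, since levels 2, 1 and -1 all use 75 mg.
- Note (6): 75 × 14 = 1050 mg (1050/2100 = 50%).

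*Recurrence, axitinib started at 5 mg twice daily (planned 5 × 2 × 28 = 280 mg), already reduced to 3 mg:*
- Note (3): 0 mg.
- Dose reduction paragraph: 2 × 2 × 28 = 112 mg (112/280 = 40%).

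*Grade 4 attributed to palbociclib at 125 mg:* note (3) 0 mg; Dose reduction paragraph 100 × 21 = 2100 mg; note (6) 125 × 14 = 1750 mg.

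*Grade 4 of unclear cause at level 4:* note (3) no drug; restart at level 3 gives palbociclib 2100 mg and an unchanged axitinib 280 mg.

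**Limits elsewhere in section 3.3.1.**
- Avelumab: its adverse-reaction rules require permanent discontinuation for most Grade 4 and for recurrent Grade 3 reactions.
- Axitinib: its toxicity guidance requires discontinuation for reversible posterior leukoencephalopathy syndrome, and for severe hypertension persisting despite treatment and dose reduction. For gastrointestinal bleeding, perforation, proteinuria and thromboembolism, all named in the DLT list, it gives only caution, monitoring, interruption or reduction.
- CMC: it confirms DLTs, may help with attribution, and under note (2) meets at least monthly to manage toxicity. None of these roles ranks the rules.

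**The case against.** The best defence is that note (3) governs. It is mandatory and grade-specific, and its only stated exception is hematologic, so a site that follows it complies. The Dose reduction paragraph can be read as supplying the restart step missing from note (3)'s general instruction to hold all three drugs when the cause is unclear. Note (6) can be read as covering severe events that are not confirmed DLTs, and patients already at 75 mg who have no lower level.

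For Grade 4 this largely stands. A reader might infer three equal contradictions from the overlap; the documents do not support that, because the Grade 4 texts can be read together. What remains there is that no sentence says so.

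For recurrence the defence is weaker. The second-reduction sentence arises from a DLT, and most listed non-hematologic DLTs are Grade 3 or 4. If note (3) always prevailed, that sentence would have little left for a single drug beyond recurrences of lower grade. Note (6), headed as the specific palbociclib rule, also supports the opposite inference about precedence.

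It is also fair that the responder provision is an exception already in writing, though its CMC review attaches to stopping one drug and continuing two, not to continued reduction.

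A reader might take the frequency in note (5), fatigue and infections among palbociclib reactions of Grade 3 or more at 2% or above, as a count of affected patients. It is not: it includes first Grade 3 events, which raise no permanent-stop conflict, and says nothing about which events would be confirmed DLTs, Grade 4 or recurrent.

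**Conclusion.** The concern holds for recurrence and, in weaker form, for Grade 4. After a non-hematologic DLT attributed to one drug recurs at Grade 3 or greater, the protocol both orders a permanent stop and permits further dosing. Exposure is mainly palbociclib and those axitinib DLTs without their own stop rule.

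Per patient, the gap is between no drug and 50 to 60% of the planned 28-day palbociclib dose, or 40% for axitinib, in the recurrence examples worked above. These figures rest on the stated readings of the dose table; the 125 and 100 mg examples apply only if those levels are used. The documents give no basis for the number of patients affected.

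A reader might infer that dose-finding or the Phase 2 operating characteristics are distorted. They are not. The conflict concerns treatment after a DLT has been counted, and the boundaries in section 7.3 count patients with a DLT, so re-dosing the same patient adds nothing. Power and error rates do not change. This is an inconsistency between stated safety rules that deserves a wording correction.

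**What to change.** Amend section 3.3.1 as follows.

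1. In the Dose reduction paragraph, limit the second reduction in non-responders to recurrences below Grade 3, or state that note (3)'s permanent stop governs recurrence at Grade 3 or greater.
2. In that paragraph's restart and single-drug reduction sentences, except Grade 4 and refer to note (3).
3. Limit note (6)'s second bullet to events that are neither Grade 4 DLTs nor recurrences of a DLT at Grade 3 or greater.
4. Keep the responder provision, cross-reference it in note (3) as an exception, and make continued reduction after a recurrence at Grade 3 or greater subject to CMC review.

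The cost is a protocol amendment and a site letter, with no change to sample size, visits or analyses. The clinical price is that a few non-responders lose the option of a second reduction.
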